10.3 Local Failure

CONFIDENTIAL

This document is confidential. Do not disclose or use except as authorized.

Local failure is defined as: evidence of tumor growth/regrowth in any direction beyond that present of the pre-treatment imaging studies in the treated lesion(s). Intrahepatic recurrence elsewhere in the liver is defined as any new lesion in the liver. The imaging studies are to be comparable in technical factors.

10.4 Marginal failure

Marginal failure is defined as appearance of tumor growth at the margin of the target volume

10.5 Nodal failure

Failure in regional lymph nodes: porta-hepatis, para-aortic, diaphragmatic.

10.6 Distant Failure

Defined as appearance of tumor at sites beyond regional nodal and marginal site.

10.7 Overall Survival

Duration measured from registration until death or censored at date of last follow-up for patients still alive.

11. ADVERSE EVENT REPORTING REQUIREMENTS

Adverse Events

As above, the CTCAE 3.0 will be used to grade all acute and late radiation effects and Adverse Events.

Report of Adverse Events to the IRB

Adverse events will be reported to each site's IRB in accordance with the local IRB guidelines. All adverse events will also be reported to the Coordinating Center and all participating sites as described in the attached Data and Safety Monitoring Plan (Appendix III).

11.1 General

Adverse event collection and reporting is a routine part of every clinical trial. This study will use the descriptions and grading scales found in the NCI Common Terminology Criteria for Adverse Events version 3.0 (CTCAE v3.0) that is available at <http://ctep.cancer.gov/reporting/ctc.html>

Information on all adverse events, whether reported by the participant, directly observed, or detected by physical examination, laboratory test or other means, will be collected, recorded, followed and reported as described in the following sections.

Adverse events experienced by participants will be collected and reported from initiation of study intervention, throughout the study, and within 30 days of the last study treatment. Participants who experience an ongoing adverse event or related to a study procedure and/or study treatment beyond 30

CONFIDENTIAL

This document is confidential. Do not disclose or use except as authorized.

days will continue to be contacted by a member of the study team until the event is resolved, stabilized, or determined to be irreversible by the participating investigator.

Participants should be instructed to report any serious post-study event(s) that might reasonably be related to participation in this study. The investigator should notify the IRB, the Coordinating Center and any other applicable regulatory agency of any unanticipated death or adverse event occurring after a participant has discontinued or terminated study participation that may reasonably be related to the study.

11.2 Definitions

11.2.1 Adverse Event (AE)

An adverse event is any undesirable sign, symptom or medical condition or experience that develops or worsens in severity after starting the first dose of study treatment or any procedure specified in the protocol, even if the event is not considered to be related to the study.

Abnormal laboratory values or diagnostic test results constitute adverse events only if they induce clinical signs or symptoms or require treatment or further diagnostic tests.

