6.2 Anticipated Toxicities

CONFIDENTIAL

This document is confidential. Do not disclose or use except as authorized.

A list of the adverse events and potential risks associated with the agents administered in this study appear below and will determine whether dose delays and modifications will be made or whether the event requires expedited reporting **in addition** to routine reporting.

CAEPRs for Proton Beam Radiotherapy to the Liver

Very likely: These symptoms usually recover in the first few weeks following completion of radiation therapy

- Irritation, redness and discoloration of the skin in the radiation area.
- Fatigue (tiredness)

Likely

- Decreased blood counts
- Low platelet count
- Elevated LFTs
- Abdominal pain or cramps
- Nausea

Less likely

- Diarrhea
- Decreased/ loss of appetite
- Vomiting
- Slow wound healing
- Weight loss
- Indigestion
- Gastritis
- Radiation Esophagitis
- Rib microfracture

Rare

- Damage to the liver which could result in inflammation and scarring of the liver. This could lead to jaundice and possibly cirrhosis. Efforts to prevent excessive liver irradiation will be made to minimize the chance of these side effects
- While radiation can cause mucosal ulceration, other tissues may be damaged which may require surgery and may be life-threatening.
- Stomach and bowel are protected well from excessive dose of radiation. However, overdosing the stomach or bowel can lead to ulceration or perforation.

CONFIDENTIAL

This document is confidential. Do not disclose or use except as authorized.

- Pain, inflammation or scarring of your kidneys, stomach and bowel. These organs are protected well from excessive dose of radiation. Therefore, it is unlikely that patients will experience symptoms of injury to these organs
- Nerve damage
- Development of a new cancer resulting from treatment may happen many years after completing treatment
- Spinal cord injury

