6.4 Dose Modifications/Delays

Grade 3 or 4 acute toxicity will result in a treatment break until it resolves to Grade 2 or less, with the exception of any Grade 3 Baseline labs that fit the eligibility criteria. Thrombocytopenia will only result in a treatment break if it becomes a Grade 4. All labs will be assessed by the treating physician to determine whether they are considered clinically significant or not clinically significant and treatment will be held at their discretion. If a treatment break of > 14 days is needed, the patient will be removed from study.

7. DRUG FORMULATION AND ADMINISTRATION: Not applicable

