10. MEASUREMENT OF EFFECT

10.1 Toxicity and Complications

Acute and late morbidity of radiation treatment will be scored using the Common Terminology Criteria for Adverse Events 3.0 (CTCAE 3.0; see Appendix 11)

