11.5.2 Non-Serious Adverse Event Reporting Requirements

Non-serious adverse events will be reported to the Principal Investigator on the toxicity Case Report Forms.

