14.4 Analysis of Secondary Endpoints

The secondary endpoints of acute and late toxicity, tumor response, failure patterns and overall survival are defined in the modality review of 10.1-10.7. Toxicity and response data will be summarized in tables, with the exact binomial confidence interval reported for their rates. Time to failure and survival will be analyzed using standard methods for failure time data, primarily the Kaplan-Meier estimate, while differences between patient subgroups may be explored using the log-rank test. In particular, the increase in sample size will provide high precision for estimating the failure and survival endpoints separately for patients with hepatocellular cancer and cholangiocarcinoma.

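### Two recording rules for laboratory abnormalities feed one toxicity form with no stated precedence, and Grade 3 values allowed at entry blur the grades

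*Combined protocol and SAP*

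**What the plan says.** Two parts of the protocol bear on whether an abnormal laboratory result is written down as a harm.

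- **Toxicity.** Section 10.1 states: "Acute and late morbidity of radiation treatment will be scored using the Common Terminology Criteria for Adverse Events 3.0". Section 6.1 supplies the collection rule: Grade 2 or above and at least possibly related, entered on the toxicity case report form from first treatment to the final study visit. Neither section asks for symptoms or action. Section 6.2 lists "Elevated LFTs" and "Low platelet count" among the likely effects, together with decreased blood counts.
- **Adverse events.** Section 11.2.1 states: "Abnormal laboratory values or diagnostic test results constitute adverse events only if they induce clinical signs or symptoms or require treatment"; the sentence ends by adding a need for further diagnostic tests. Section 11.5.2 adds: "Non-serious adverse events will be reported to the Principal Investigator on the toxicity Case Report Forms".

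On baseline values, Section 3.1.7 admits patients with bilirubin up to 4.0 times and AST/ALT up to 6.0 times the upper limit of normal, and with platelets down to 25,000/mcL. Section 6.4 makes its treatment-break rule "with the exception of any Grade 3 Baseline labs that fit the eligibility criteria", so the protocol itself expects some patients to start at Grade 3.

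On analysis, Section 14.4 takes the definition of acute and late toxicity from Section 10 and says: "Toxicity and response data will be summarized in tables, with the exact binomial confidence interval reported for their rates". It mentions no comparison with baseline.

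**The concern.** Three of the five effects in the likely category of 6.2 are laboratory findings: decreased counts, low platelets and raised liver tests. Such changes can occur without symptoms. If a site uses 11.2.1 to decide what goes on the toxicity form, it can leave off a change that a site using 6.1 would enter. A rate pooled over three proton centres would then mix two case definitions, and an exact binomial interval does nothing to correct that.

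Safety and tolerance is secondary objective 1.3.1. The liver is the organ that the EUD and mean-dose limits in Section 5.1.2.3 are there to protect. A reader of the final report will want to know how often liver function worsened after treatment. Raw grades entered under an unclear rule, in patients some of whom began at Grade 3, do not answer that.

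**Working it through.** The plan states no toxicity rate, safety boundary or safety sample size, so there is no figure to reproduce. The check is a comparison of the rules, followed by an illustration.

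**Step 1. Apply both rules to a symptom-free laboratory worsening of Grade 2 or above.** Action here means that treatment or further diagnostic tests are required.

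| Judged at least possibly related? | Action required? | Entered under 6.1 | Adverse event under 11.2.1 |
|---|---|---|---|
| Yes | Yes | Yes | Yes |
| Yes | No | Yes | No |
| No | Yes | No | Yes |
| No | No | No | No |

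Row 2 is where sites can differ, because both rules lead to the same form and the available text does not rank them. Row 4 is lost whichever rule is followed. An example is a bilirubin rise attributed to cirrhosis and simply watched. Section 11.5.1 calls for Grade 4 events to be reported up to 30 days after the last treatment without an attribution condition, so the row 4 gap is clearest at Grades 2 and 3 and in later follow-up.

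**Step 2. Look for the source of the toxicity tables.** Section 14.4 points to 10.1, and 10.1 names a grading scale. Neither says whether cases come from form entries or from the laboratory values. If they come from the form, anything kept off the form is absent from the table.

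**Step 3. Look at the data that are scheduled.** From Sections 9.1 and 9.2:

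- Bilirubin and AST/ALT: before entry, weekly on treatment, and at every follow-up visit.
- Albumin, PT/INR and Child-Pugh: before entry and at every follow-up visit. There are 9 visits from month 1 to month 24 and 6 from month 30 to month 60, so 15 in all.
- CBC (platelets, ANC): before entry and weekly on treatment only.

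Child-Pugh is thus collected repeatedly, but Sections 10 and 14 make no use of it.

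**Step 4. Illustrate the size.** The total of 90 patients is from Section 14.2. The true rate and the capture fraction are assumptions. Recorded count = 90 × true rate × capture fraction, as a whole number, with the exact 95% interval that 14.4 names.

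| Assumed true rate | Capture | Recorded | Exact 95% interval |
|---|---|---|---|
| 20% | 100% | 18/90 = 20.0% | 12.3% to 29.8% |
| 20% | 75% | 14/90 = 15.6% | 8.8% to 24.7% |
| 20% | 50% | 9/90 = 10.0% | 4.7% to 18.1% |
| 10% | 100% | 9/90 = 10.0% | 4.7% to 18.1% |
| 10% | 50% | 4/90 = 4.4% | 1.2% to 11.0% |
| 40% | 100% | 36/90 = 40.0% | 29.8% to 50.9% |
| 40% | 50% | 18/90 = 20.0% | 12.3% to 29.8% |

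At a true rate of 20%, half capture gives an interval that excludes the assumed truth, and 75% capture does not. The half-capture rows describe average capture over all centres. Suppose instead three equal centres of 30 with 6 true events each, two capturing all and one capturing half. The recorded total is 6 + 6 + 3 = 15, and 15/90 = 16.7%.

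**The case against.** The strongest reply is that the two rules add together. Section 6.1 has its own instruction for the toxicity form and itself names liver-test and count changes as acute side effects. Section 11.5.2 adds adverse events to that form and removes nothing. Section 11.2.1 says when a laboratory value is an adverse event, not when it is a toxicity, and the opening of Section 11 names radiation effects and adverse events separately. On this reading, a site that omits a related Grade 3 bilirubin rise breaches 6.1. Moreover, 14.4 ties the endpoint to 10.1, and the further-tests limb of 11.2.1 is wide enough to bring in many abnormal results.

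Most of this stands. A reader might infer that laboratory and liver toxicity will be under-counted. The documents do not support that, because a site can obey both rules and then loses no related Grade 2 or higher event. What the reply does not supply is a sentence saying that the rules are additive, or any capture of row 4. Whether a raised value requires further tests, when liver tests are already repeated on schedule, is also a local judgement.

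On baseline, it is fair to say that an adverse event must be new or worse after treatment starts, that 6.1 requires attribution, and that baseline values are collected. These safeguards depend on judgement at the time of entry. None puts a baseline comparison into the 14.4 tables.

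Finally, Section 11 refers to a Data and Safety Monitoring Plan, which is not in the text available. It may contain a precedence rule, so the statement that none exists is limited to what can be read here.

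**Conclusion.** The point holds as an ambiguity with a real but unquantified risk. Two rules for laboratory abnormalities share one form, and no available text ranks them. Symptom-free laboratory toxicity may therefore be under-recorded and may be recorded differently by site. Even under uniform use of 6.1, unrelated symptom-free worsening that requires no action meets neither rule. Separately, a raw grade does not distinguish new liver injury from the state at entry.

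The size cannot be derived from the documents. Under an assumed 20% true rate in 90 patients, the recorded rate runs from 20% if capture is complete to 10% if half is captured. The lower end needs half capture averaged over all centres and should not be read as a forecast. The loss is also recoverable to the extent that the scheduled values are entered in the database.

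The 2-year local control endpoint and its sample size are not affected. The change is worth making because safety is a stated objective and the remedy uses scheduled data.

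**What to change.** - In 10.1 and 14.4, state that laboratory toxicity is graded by CTCAE from the scheduled laboratory values, regardless of symptoms, attribution or adverse-event status.
- In 11.2.1, limit the symptom-or-action condition to adverse-event reporting.
- In 14.4, add the worst post-baseline grade and the baseline-to-worst shift for bilirubin and AST/ALT over treatment and follow-up. Give the same for platelets and ANC over the treatment period only, since CBC is not scheduled in follow-up.
- Summarise the change in Child-Pugh score from baseline at each follow-up visit as a descriptive liver-safety measure. If a threshold for worsening is wanted, the sponsor should prespecify it; the documents give none.
- Check that the Data and Safety Monitoring Plan and the form completion instructions agree with the revised text.

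The cost is wording in three sections and table programming on data that Section 9.1 already lists as required. No visit, test or treatment rule changes. Reported toxicity rates may look less favourable than under form-based counting.

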11.2.2 Serious adverse event (SAE)

A serious adverse event is an undesirable sign, symptom, or medical condition which:

- is fatal or life-threatening;
- requires or prolongs inpatient hospitalization;
- results in persistent or significant disability/incapacity;
- constitutes a congenital anomaly or birth defect; or
- jeopardizes the participant and requires medical or surgical intervention to prevent one of the outcomes listed above.

Events **not** considered to be serious adverse events are hospitalizations for:

- routine treatment or monitoring of the studied indication, not associated with any deterioration in condition, or for elective procedures
- elective or pre-planned treatment for a pre-existing condition that did not worsen
- emergency outpatient treatment for an event not fulfilling the serious criteria outlined above and not resulting in inpatient admission
- respite care

11.2.3 Expectedness

Adverse events can be 'Expected' or 'Unexpected'.

11.2.3.1 Expected adverse event

Expected adverse events are those that have been previously identified as resulting from administration of the treatment. For the purposes of this study, an adverse event is considered expected when it appears in the protocol and/or informed consent document as a potential risk.

Refer to Section 6.1 for a listing of expected adverse events associated with the study treatment.

11.2.3.2. Unexpected adverse event

For the purposes of this study, an adverse event is considered unexpected when it varies in nature, intensity or frequency from information provided in the protocol and/or informed consent document as a potential risk.

11.2.4 Attribution

Attribution is the relationship between an adverse event or serious adverse event and the study treatment. Attribution will be assigned as follows:

- Definite – The AE is clearly related to the study treatment.
- Probable – The AE is likely related to the study treatment.
- Possible – The AE may be related to the study treatment.
- Unlikely - The AE is doubtfully related to the study treatment.
- Unrelated - The AE is clearly NOT related to the study treatment.

11.3 Recording Adverse Events

Adverse event information will be obtained at each contact with the participant. All adverse events will be recorded on the appropriate study-specific case report forms (CRFs).

11.4 Reporting Adverse Events

For multi-site trials where a DF/HCC investigator is serving as the principal investigator, each participating investigator is required to abide by the reporting requirements set by the DF/HCC. The study must be conducted in compliance with FDA regulations, local safety reporting requirements and reporting requirements of the principal investigator.

Each adverse event will be assessed to determine if it meets the criteria for serious adverse event. If a serious adverse event occurs, expedited reporting will follow local policies, and federal guidelines and regulations as appropriate.

It is the responsibility of the participating investigator to notify the Principal Investigator, and the local IRB of all serious adverse events as required in the protocol.

The Principal Investigator will provide information with respect to adverse events and safe use of the study treatment (e.g., safety reports, Action Letters) to all participating investigators as described in the attached Data and Safety Monitoring Plan (DSMP) as soon as the information becomes available.

11.5 Coordinating Center Notification by Investigator

11.5.1 Serious Adverse Event Reporting Requirements

All events meeting the criteria for Serious Adverse Event (see Section 11.2.2) that occur after the initial dose of study treatment, during treatment, or within 30 days of the last dose of treatment must be reported to the DF/HCC Overall Principal Investigator as serious adverse events. This includes events meeting criteria outlined in Section 11.2 as well as the following:

- Grade 2 (moderate) and Grade 3 (severe) events that are unexpected and at least possibly related/associated with the intervention.
- All Grade 4 (life-threatening or disabling) events that are unexpected or not specifically listed in the protocol as not requiring reporting
- All Grade 5 (fatal) events while the participant is enrolled and actively participating in the trial OR when the event occurs within 30 days of the last study intervention.

Note: If the participant is in long-term follow-up, report death at the time of continuing review.

CONFIDENTIAL

This document is confidential. Do not disclose or use except as authorized.

The participating investigator must report each serious adverse event, regardless attribution, to the DF/HCC Principal Investigator within 1 business day of learning of the occurrence. In the event that the participating investigator does not become aware of the serious adverse event immediately (e.g., participant sought treatment elsewhere), the participating investigator is to report the event within 1 business day after learning of it and document the time of his or her first awareness of the adverse event. Report serious adverse events by email or fax to the Coordinating Center at:

Within the following 1-2 business days, the participating investigator must provide follow-up information on the serious adverse event. Follow-up information should describe whether the event has resolved or continues, if and how the event was treated, and whether the participant will continue or discontinue study participation.

11.5.2 Non-Serious Adverse Event Reporting Requirements

Non-serious adverse events will be reported to the Principal Investigator on the toxicity Case Report Forms.

11.6 Institutional Review Board (IRB) Notification by Investigator

The participating investigator will report all adverse events and serious adverse events to the Principal Investigator (or Protocol Chair) and to the local IRB according to the local IRB's policies and procedures in reporting adverse events.

The Principal Investigator (or Protocol Chair) will report adverse events and serious adverse events from all participating sites to the DFCI IRB according to the IRB's policies and procedures in reporting adverse events.

11.7 Hospital Risk Management Notification by Investigator

The participating investigator will report to the Principal Investigator (or Protocol Chair) and to local Risk Management any subject safety reports or sentinel events that require reporting according to institutional policy.

12. DATA AND SAFETY MONITORING

12.1 Data Reporting

12.1.1 Method

Data for this study will be collected and managed by the MGH Biostatistics Center. Electronic Case Report Forms will be posted for use by all participating sites in TrialDB, and study staff at each site will be given access to enter CRF data electronically. Data will be monitored by the MGH FHBPTC Senior Clinical Research Program Manager or designee.

12.1.2 Data Submission

The schedule for completion and submission of electronic case report forms to the MGH Biostatistics Center can be found in section 5.10 in the Data Safety Monitoring Plan.

12.1.3 DICOM Data

De-identified DICOM data from the proton plans for each study subject will be transmitted to the Advanced Technology Consortium QA Center at Washington University, St. Louis (ATC). ATC will maintain the de-identified image data for analysis by investigators at all participating sites. Treatment plans for all patients will be sent electronically to the ATC. The treatment planner or the physicist who performs the initial review of the plan will be responsible for transmitting these data. Please see section 12.3.1 for more information.

